8.6.5. Safety Laboratory Tests

Blood and urine samples for clinical safety laboratory assessments will be collected at the time points designated in [Table 1](#) at Screening and Day 1. After Day 1, clinical safety laboratory assessments are to be collected per SOC. Note that if screening safety laboratory assessments are performed within 2 days of Day 1, then the pre-dose Day 1 safety laboratory assessments need not be repeated.

These samples will be analyzed at the local laboratory following their laboratory standard operating procedures (SOPs).

The following parameters may be collected and documented in the eCRF, as available per SOC:

- Clinical chemistry (serum quantitatively):
 - Total bilirubin, alkaline phosphatase, aspartate aminotransferase (AST), alanine aminotransferase (ALT), lactate dehydrogenase (LDH), creatine phosphokinase, albumin, creatinine, blood urea nitrogen, total protein, glucose, , sodium, potassium, calcium and chloride,.
- Hematology (blood quantitatively):
 - Leukocytes, erythrocytes, hemoglobin, hematocrit, thrombocytes, partial automated differentiation (lymphocytes, monocytes, eosinophils, basophils, neutrophils), mean corpuscular volume, mean corpuscular hemoglobin, mean corpuscular hemoglobin concentration
- Coagulation (blood quantitatively):
 - Prothrombin time (reported in seconds and as international normalized ratio) and partial thromboplastin time
- Urinalysis (semi-quantitative by dipstick):
 - Hemoglobin, urobilinogen, ketones, glucose, protein
 - Microscopy is to be performed if indicated by an abnormal and clinically significant result. Culture results, if conducted per SOC, are to be documented.

- Cardiac troponins, ferritin, B-type natriuretic peptide (BNP) or N-terminal-pro-BNP, and D-dimer.

In case of unexplained or unexpected clinical laboratory test values, the tests will be repeated as soon as possible and followed up until the results have returned to the normal range, baseline level and/or an adequate explanation for the abnormality is found. The clinical laboratory will clearly mark all laboratory test values that are outside the normal range and the Investigator will indicate which of these deviations are clinically significant. These clinically significant deviating laboratory results will then be recorded as AEs and the relationship to the treatment will be indicated (see also [Section 9.2](#)).

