Continuous data will be summarized in terms of the mean, standard deviation (SD), median, minimum, maximum and number of observations, unless otherwise stated. Continuous data that are expected to be skewed will be presented in terms of the maximum, upper quartile, median, lower quartile, minimum and number of observations. The minimum and maximum will be reported to the same number of decimal places as the raw data recorded in the database. The mean, median, lower quartile and upper quartile will be reported to one more decimal place than the raw data recorded in the database. The SD will be reported to two more decimal places than the raw data recorded in the database. In general, the maximum number of decimal places reported shall be four for any summary statistic.

Categorical data will be summarized in terms of the number of patients providing data at the relevant time point (n), frequency counts and percentages. Any planned collapsing of categories will be detailed in the SAP text and the data displays.

Percentages will be presented to one decimal place. Percentages will not be presented for zero counts. Percentages will be calculated using N as the denominator, unless otherwise stated. If sample sizes are small, the data displays will show the percentages, but any textual report will describe frequencies only. Changes from baseline in categorical data will be summarized using shift tables where appropriate.

P-values greater than or equal to 0.001, in general, will be presented to three decimal places. P-values less than 0.001 will be presented as “<0.001”. Confidence intervals (CIs) will be presented to one more decimal place than the raw data.

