## **4.3 Missing Data**

### **4.3.1 Imputation of Non-Date Missing Data**

Missing data occurs when any requested data is not provided, leading to blank fields on the collection instrument. These data will be indicated by the use of a “blank” in subject listing displays. Answers such as “Not applicable” and “Not evaluable” are not considered to be missing data and should be displayed as such.

Subjects with the designation of treatment relationship for AEs and SAEs missing will have the worst realistic case assumed to impute the relationship: if relationship is missing and the AE started on or after study drug administration it will be assumed to be “related” (worst case). If the AE with missing relationship started before study drug administration (eg, during Screening Period), it will be considered as “not related” (realistic case). Missing Severity will be assumed to be “Life-threatening” (worst case). In listings these imputed relationships and causalities will be flagged.

For variables which determine the proportion of events, all subjects in the respective analysis set will be included in the denominator when calculating the percentages irrespective of whether their outcome may be missing.

Handling of complete or partial missing dates for Adverse Events or reported Concomitant Medication will be given in the following Section.

All other missing data will not be imputed.

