Number and percentage of patients who died will be summarized by day 14, 28 and 60 by treatment group. If the total number  $\leq 3$ , only listing will be presented.

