#### 4.10.3 Clinical Laboratory Evaluation

Local laboratories will be used for laboratory safety evaluations in this study. [Table 6](#) shows the list of laboratory parameters. Laboratory results will be graded as low, normal, or high comparing to the normal range provided by the local laboratories .

All laboratory values will be reported in local units and in alphabetical order.

For by-visit summaries, the first non-missing assessment (including repeat assessments) recorded at each visit will be used. Optional laboratory parameters (Creatine Phosphokinase, Lactate Dehydrogenase (LDH)) will not be summarized by treatment group, only listed. Separate summaries for Hematology, Clinical Chemistry, Coagulation, Urinalysis and Serology (Baseline only) to be produced will be:

- for laboratory values reported as a character value, such as 'negative', number and percentage of subjects for each outcome by scheduled visit
- for continuous laboratory values, number and percentage of subjects with values outside normal range by scheduled visit,
- for continuous laboratory values, shifts from baseline in relation to normal range at all scheduled visits.

By-patient listings of all laboratory data, with abnormal values flagged, will be provided for Serology, Hematology, Clinical Chemistry, Coagulation and Urinalysis test results. Further marker of anaphylaxis: Tryptase will be listed by subject.

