#### 4.11.2 Immunogenicity

Anti-Drug Antibody (ADA) and Jo-1 Ab data will be summarized by treatment group for the Safety Set.

The following will be summarized for ADA:

- At Baseline
  - ADA incidence and incidence rate for Screened Positive, Confirmed Positive,
  - ADA titer value for positive results categorized (1:30 to <1:90, 1:90 to <1:270,  $\geq 1:270$ ).
- By Visit (after study drug administration)
  - ADA incidence and incidence rate for Screened Positive, Confirmed Positive,
  - ADA titer value or positive results categorized (1:30 to <1:90, 1:90 to <1:270,  $\geq 1:270$ ).
- At Any Visit (after study drug administration)
  - ADA incidence and incidence rate for at least one Confirmed Positive result,
  - Maximum ADA titer value or positive results categorized (1:30 to <1:90, 1:90 to <1:270,  $\geq 1:270$ );
  - Baseline ADA Incidence (The proportion of pre-dose ADA-positive subjects as a percentage of total number of subjects (ATYR1923 and placebo subjects))
  - Treatment-induced ADA Incidence (The proportion of individuals with Confirmed Positive ADA any time after ATYR1923 treatment that were ADA negative at baseline),
  - Treatment-boosted ADA Incidence (The proportion of individuals that were ADA positive at baseline who had a greater value in ADA after ATYR1923 treatment compared to baseline).

The following will be summarized for Jo-1 Ab:

- incidence and incidence rate of results that were above 'high' compared to local normal range by visit and at any visit,
- incidence and incidence rate of results that were abnormal (above 'high' or below 'low' compared to local normal range) by visit and at any visit.

ADA and serum Jo-1 Ab will be listed separately by subject including nominal/planned visits and actual time after start of study drug administration.

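### By-visit laboratory, ADA and Jo-1 percentages are taken over all patients, tested or not, so they are lower bounds that fall as patients are discharged and can differ between arms through discharge timing alone

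*SAP*

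**What the plan says.** Two rules fix the denominator. SAP 4.3.1 says that, for variables giving a proportion of events, all subjects of the analysis set "will be included in the denominator when calculating the percentages irrespective of whether their outcome may be missing". It adds that "All other missing data will not be imputed", apart from the adverse-event and date rules in SAP 4.3. SAP 4.2 is broader: "Percentages will be calculated using N as the denominator, unless otherwise stated". The same section has categorical tables show the "number of patients providing data at the relevant time point (n), frequency counts and percentages", so n with data appears beside a percentage based on N.

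The sections that use these rules set no by-visit denominator of their own. SAP 4.10.3 asks for the "number and percentage of subjects with values outside normal range by scheduled visit". SAP 4.11.2 asks for ADA and Jo-1 incidence by visit and at any visit, including "ADA incidence and incidence rate for at least one Confirmed Positive result". For mortality, SAP 4.9.4.1 says "Number and percentage of patients who died will be summarized by day 14, 28 and 60 by treatment group", with a listing only if the total is 3 or fewer.

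On data collection, Protocol 8.6.5 says "After Day 1, clinical safety laboratory assessments are to be collected per SOC". Protocol 4.1 and SAP 3.1.1 make the visits after discharge telephone contacts: Day 7 (as applicable) and Day 14 for early discharges, then Days 28 and 60.

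**The concern.** A patient who has gone home has no planned blood result at a later visit. Under a fixed N, that patient is printed as not abnormal or not antibody-positive. Nothing is formally imputed, but the arithmetic is the same as imputing a negative result.

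For recovery by Day 14 or 28, the fixed denominator counts a missing outcome as not recovered, which is conservative. For a laboratory abnormality or an antibody it runs the other way. It also runs against SAP 4.3.1's own approach to adverse events, where a missing severity or a missing post-dose relationship is set to the unfavourable value.

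The missing results are tied to discharge, and time to discharge is a secondary endpoint that treatment may change. If one arm goes home sooner, its by-visit percentages fall sooner, with no difference in laboratory or antibody findings behind it.

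**Working it through.** **Inputs from the documents.** There are 30 patients randomized 1:1:1 (SAP 3.1.4), so N = 30/3 = 10 per arm, taking all as dosed. The denominator rules are in SAP 4.2 and 4.3.1. The documents give no expected abnormality rate, discharge rate or dropout rate, so there is no planned figure to reproduce.

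**Assumed inputs.** These are n, the number tested at a visit, and x, the number abnormal or positive among them. They are varied below.

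**Formulas.**
- Percentage under the SAP: x/N = (x/n) × (n/N).
- Percentage among those tested: x/n.
- Possible range for all N patients: from x/N (every untested patient negative) to (x + N − n)/N (every untested patient positive).

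**Step 1: one arm, 50% positive among those tested.**

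| Tested n | Positive x | SAP x/N | Tested x/n | Range for all 10 |
|---|---|---|---|---|
| 10 | 5 | 50% | 50% | 50–50% |
| 8 | 4 | 40% | 50% | 40–60% |
| 6 | 3 | 30% | 50% | 30–70% |
| 4 | 2 | 20% | 50% | 20–80% |
| 2 | 1 | 10% | 50% | 10–90% |

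The SAP percentage is always the lower end of the range. It equals the all-patient rate only if every untested patient is negative.

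**Step 2: two arms with the same rate among those tested.** The factor n/N passes straight into the comparison.
- 50% positive, 8 of 10 placebo and 4 of 10 active patients tested: 4/10 = 40% against 2/10 = 20%.
- 40% abnormal, 6 of 10 placebo and 3 of 10 active patients tested: 0.40 × 6/10 = 24% against 0.40 × 3/10 = 12%. The ranges are 24% to (2.4 + 4)/10 = 64% for placebo, and 12% to (1.2 + 7)/10 = 82% for active. The 2.4 and 1.2 are expected counts, not whole patients.

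In both cases the printed two-fold difference comes only from how many patients were tested.

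**Step 3: do the visit windows close the gap?** Only in part. SAP 4.2, Table 3, maps unscheduled discharge visits on Day 8 to Day 7, Days 9–11 to Day 10, Days 12–16 to Day 14, Days 23–33 to Day 28 and Days 55–65 to Day 60. A discharge on Days 17–22 or 34–54 falls in no window, and SAP 4.2 leaves unmapped discharge visits out of the summaries. A mapped discharge result fills one visit and none after it. Table 2 maps telephone visits, for which no blood result is planned.

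**Step 4: mortality.** With d known deaths and u patients of unknown status, the plan prints d/N and the bounds are d/N to (d + u)/N. For d = 1 and u = 1, 2 or 3, the plan prints 10% and the bounds are 10–20%, 10–30% or 10–40%. For d = 2 and u = 2, it prints 20% and the bounds are 20–40%. The values of u are assumptions.

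**The case against.** **The reach of SAP 4.3.1 is arguable.** It speaks of proportions of events and defines missing data as requested data not provided. A laboratory category may not be an event, and a blood test may not be requested at a telephone contact. That stands as a reading of 4.3.1, but the N default in 4.2 leads to the same denominator.

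**The plan already softens the problem.** Tables show n, all results are listed by patient, and 4.2 limits text to frequencies when samples are small, which fits about 10 per arm. A careful reader could recompute x/n. This lowers the stakes, but the percentage in the table would still be on N.

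**The rate among tested patients is not the truth either.** This stands in full. A reader might infer from Step 2 that 40% is the correct value in both arms. The documents do not support that: it is the rate among patients still in hospital, a selected and probably sicker group. If one arm discharges faster, its remaining inpatients may be its sickest, and x/n could then make that arm look worse.

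**The primary objective is safety.** A reader might infer that the primary result is understated. It is not. The primary endpoint is TEAE incidence, for which all dosed patients are the usual denominator. Adverse events are collected through the last visit, and Protocol 8.6.5 has clinically significant laboratory deviations recorded as adverse events.

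**Any-visit ADA.** A reader might extend the criticism to this summary. It is largely protected, because the Day 14/Discharge assessments are done at discharge, and SAP 4.11.2 describes treatment-induced and treatment-boosted ADA by baseline status. What remains is to state the denominators.

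**Mortality.** A reader might infer that the plan needs a Kaplan–Meier analysis. Deaths over all treated patients is a conventional display, percentages appear only with more than 3 deaths, and no loss rate is given. Only the silence on unknown vital status remains.

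**Conclusion.** The concern holds for the by-visit laboratory, ADA and Jo-1 percentages. As written, the SAP divides by all patients in the analysis set, although those already discharged have no planned blood result. The printed figure is a lower bound that falls with discharge. In the illustrations it differs two-fold between arms (12% against 24%, or 20% against 40%) with identical rates among those tested. The ranges of 12–82% and 24–64% show how little such figures say about all patients at a late visit.

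The numbers rest on 10 dosed patients per arm and on assumed testing fractions and rates. They show the mechanism and are not forecasts. The absence of outpatient blood results is taken from the telephone-contact wording; the extracted schedule tables are too broken to check it.

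The affected tables are supportive, in an unpowered exploratory study with no stated decision rule tied to them. The documents do not support a claim that the primary safety result is biased, or that ATYR1923 would necessarily look safer: that direction requires earlier discharge on active drug, which is an assumption.

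**What to change.** 1. In SAP 4.10.3 and 4.11.2, state that by-visit laboratory, ADA and Jo-1 percentages use patients with a result at that visit. Print x/n and the number missing, and footnote that late-visit rates describe only patients still in hospital, a selected group with small n.
2. For any-visit and treatment-induced ADA, state that the denominator is patients with the required baseline sample and at least one post-dose sample.
3. For mortality, keep deaths over all treated patients. Add the number with unknown vital status at Days 14, 28 and 60, with best-case and worst-case bounds.
4. Leave the all-dosed denominator for TEAE incidence and the fixed denominator for recovery as they are.
5. Label the change as post-unblinding, since the SAP revision history already lists post-unblinding modifications in versions 2.0 and 3.0.

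The cost is SAP wording and table shells; no new data are needed. The drawback is small late-visit denominators and a selected group, which is why the number missing must be printed beside each percentage.

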4.1.1. Assessments During Intubation

In the event that a patient requires intubation, SOC assessments and interventions will supersede study assessments for the duration of intubation, with the exception of the WHO Scale and sample collection for ADA and Jo-1 Ab, which will continue to be collected as per the Schedule of Assessments ([Table 1](#)) on Days 5, 7, 10, 14 and weekly thereafter. The following clinical assessments will be collected and analyzed as available per the institution's electronic medical records.

- Date and time of intubation and extubation.
- Adverse events (AEs) (including new infections). In the case of new infections, the site and source of culture are to be recorded.
- Concomitant medications.

Patients requiring intubation will have the assessments scheduled for Day 14 and/or Discharge performed at the time of hospital discharge and will attend Day 28 and 60 TC follow-up visits.

2 With the exception of the WHO Scale and sample collection for ADA and Jo-1 Ab, which will continue to be collected as per the Schedule of Assessments.

If the patient is hospitalized for ≥ 21 days, the Day 14 and/or Discharge assessments are to be performed weekly (Days 21, 28, 35, etc.) until discharge (with the exception of PK, which is to be done only at Day 28).

After discharge, the patient will proceed to the next scheduled outpatient TC follow-up visit. (Thus, if a patient remains hospitalized on Day 28, the Day 28 TC follow-up visit need not be conducted.)

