### 4.2 General Presentation Considerations

**Baseline:** the last available pre-treatment assessment, unless otherwise specify. All assessments should have time collected. If time is not collected and date of assessment is the same as study drug administration date then assessment will be assumed to be collected prior to treatment unless schedule of assessments and protocol indicate planned collection is always after dosing.

For baseline of oxygen use, total oxygen use in 24 hours before drug administration date.

**Day-of-Discharge (DoD):** day when patient is discharged from the hospital.

**Date of discharge:** date patient is discharged from the hospital.

**Early Termination (ET):** day when patient withdraws from the study before completion.

**End-of-Study (EOS):** the EOS assessment is at Day 60 for patients who complete the study.

**End of study date:** date of EOS assessment (Day 60) if patient completes the study or date of early withdrawal if patient discontinues early, or date of death.

**Study Day:** <Assessment Date> - study drug administration date + 1 if <Assessment Date> is on or after study drug administration date. <Assessment Date> - study drug administration date, if <Assessment Date> is before study drug administration date.

Durations are generally calculated as the stop date - start date +1, if not otherwise stated.

For elapsed time (eg, time since the initial diagnosis) is calculated as reference date - event date.

If more than one laboratory value is available for a given study day, the last valid observation will be used in summaries, unless otherwise stated. If it is not possible to determine which is the last measurement due to missing times, then the average of all measurements for that study day will be used as the value for that study day. All observations will be presented in listings.

Laboratory data will be presented in standard units.

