#### **Analysis Visit Window:**

By visit summaries will be based on the nominal/scheduled visit as reported in eCRF and will be grouped by Day 1, 2, 3, 4, 5, 6, 7, 10, 14, 28 and 60.

For (telephone contact) TC follow up visits and unscheduled Discharge visits, analysis visit windows will be applied as in [Table 2](#) and [Table 3](#) below. Note, analysis visit windows are only used for by visit summaries, not for time to event calculation which will be based on actual date of data collected. TC follow up visits and Discharge visits that are not in any of the analysis visit windows, will be excluded from summaries and only presented in listings.

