Days with fever up to Day 14 will be used as a sensitivity analysis. Days will be calculated the same as described for Days of supplemental oxygen (O2) up to Day 14.

Change from baseline in WHO Ordinal Scale score

The description of the WHO Ordinal Scale score is shown in [Section 6.2](#). The Number and percentage of patients on WHO Scale scores and change from baseline (-7, -6, -5, -4, -3, -1, 0, 1, 2, 3, 4) will be presented by visit. Shift table will be presented by visit as well.

Simple Ordinal logistic regression on the WHO Scale score at each visit (Days 5, 7, 14, 28, and 60) will be performed to compare ATYR1923 1 mg/kg versus Placebo and ATYR1923 3 mg/kg versus Placebo. Firth logistic regression ([Firth, 1993](#)) on the collapsed WHO Ordinal Scale (0-3 versus 4-8) at each visit (Days 5, 7, 14, 28, and 60) will be performed as well.

Distribution of WHO Ordinal Scale at 1, 2, 3, 4, 5, 6, 7, 10, 14, 28 and 60 days will be visualized by treatment group using an stacked bar chart. These figures will only consider scheduled assessments and in case the scheduled assessment is not available the mapped unscheduled TC follow up assessments as defined in [Section 4.2](#).

Time to Improvement in Clinical Status

Time to improvement in days is the time in which the patient sees a decrease after study treatment in the WHO Ordinal Scale score from baseline by at least 1 point, derived as:

date of decrease in WHO scale compared to baseline by at least 1 point - study drug administration date; or date of discharge from hospital - study drug administration date, whichever occurs first.

In the case that a patient has not decreased in the WHO scale or withdraws from the study, they will be censored at EOS date. Time to improvement will be analyzed using the Kaplan-Meier methods and Cox Proportional Hazards model as described in the above.

Repeat analysis above for improvement of WHO Ordinal Scale score by at least 2 points.

Additionally, time to improvement will be analyzed using an adapted derivation: date of decrease in WHO scale compared to baseline by at least 1 point - randomization date; or date of discharge from hospital - randomization date, whichever occurs first.

Related output will be noted as sensitivity analysis.

Time to improvement (by at least 1 and 2 points) will be analyzed based on mITT and EE Set. Sensitivity analysis for time to improvement will be analyzed based on mITT only.

*All-cause mortality*

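### The SAP does not say how a patient who has died is scored at later WHO visits; read literally, its missing-data rule drops that patient from the by-visit ordinal and Firth regressions

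*SAP*

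**What the plan says.** SAP 6.2 gives death the score 8. SAP 3.4.2 names change in WHO score on Days 5, 7, 14, 28 and 60 as a secondary endpoint. For it, SAP 4.9.4.1 plans the following: "Simple Ordinal logistic regression on the WHO Scale score at each visit (Days 5, 7, 14, 28, and 60) will be performed", comparing each dose with placebo. It adds a Firth logistic regression of 0-3 against 4-8 on the same days, by-visit change and shift tables, and a stacked bar chart. The population is the mITT Set (SAP 4.9.4).

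Four rules decide which scores enter:

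- SAP 4.2, visit assignment: "By visit summaries will be based on the nominal/scheduled visit as reported in eCRF". Windows apply to telephone contacts and unscheduled discharge visits (Tables 2 and 3).
- SAP 4.2, end of study: "date of EOS assessment (Day 60) if patient completes the study or date of early withdrawal if patient discontinues early, or date of death".
- SAP 4.3.1, definition: "Missing data occurs when any requested data is not provided, leading to blank fields on the collection instrument". After rules for adverse events and a pointer to the date rules, it closes: "All other missing data will not be imputed".
- SAP 4.3.1, percentages: "For variables which determine the proportion of events, all subjects in the respective analysis set will be included in the denominator", whether or not the outcome is known.

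Last observation carried forward appears in the SAP's abbreviation list, but no rule uses it. Protocol 10.1.2.4 leaves missing data to the SAP.

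**The concern.** Death is a level of this outcome, so a death before Day 14 determines the score at Days 14, 28 and 60. If the data set has no record for that patient on those days, the models estimate a contrast among survivors, and survival may itself depend on treatment. An arm with more deaths loses its worst outcomes and can look equal or better. An arm with fewer deaths gets no credit for them.

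This matters more here than it would elsewhere in the plan. Time to discharge, recovery and improvement censor a patient who dies without the event, either at death or at an end-of-study date that is the date of death. The by-visit WHO regressions are the only planned efficacy models in which death can count as the worst outcome.

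**Working it through.** The plan gives no figure to reproduce: SAP 3.1.4 sets 30 patients, 1:1:1, with no power calculation. The check is a trace through the rules, followed by illustrations.

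**1. Trace.** Take a patient who dies on Day 10.

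- Follow-up ends that day, so no Day 14, 28 or 60 visit takes place.
- If a discharge record carries score 8, Table 3 maps it to Day 10, which is not a regression day.
- SAP 4.3.1 bars filling the later days. The patient is absent from the Day 14, 28 and 60 models.
- The windows within each table do not overlap (Table 3: Day 8, Days 9-11, 12-16, 23-33 and 55-65). One death record can therefore be mapped to at most one analysis visit. A Day 14 death kept at Day 14 is still lost at Days 28 and 60.
- The same gap applies at Days 5 and 7 for earlier deaths.
- The bar chart admits only scheduled assessments or mapped telephone contacts.

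**2. Firth odds ratio.** With arm as the only term, the Firth estimate equals adding 0.5 to each cell. Let a and b be the active patients at 0-3 and 4-8, and c and d the same for placebo:

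OR = [(a+0.5)/(b+0.5)] / [(c+0.5)/(d+0.5)]

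The inputs are 10 per arm (30/3, from SAP 3.1.4) and assumed death counts, because the documents give no mortality rate. For two placebo deaths with every survivor at 0-3:

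- Deaths dropped, 10/10 against 8/8 in the regression data set: (10.5/0.5)/(8.5/0.5) = 21/17 = 1.24.
- Deaths scored 8, 10/10 against 8/10: (10.5/0.5)/(8.5/2.5) = 21/3.4 = 6.18.

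| Deaths, active / placebo | Survivors at 4-7, each arm | OR, deaths dropped | OR, death = 8 |
|---|---|---|---|
| 0 / 1 | 0 | 1.11 | 3.32 |
| 0 / 2 | 0 | 1.24 | 6.18 |
| 0 / 3 | 0 | 1.40 | 9.80 |
| 2 / 0 | 0 | 0.81 | 0.16 |
| 0 / 2 | 1 | 1.27 | 2.96 |
| 1 / 1 | 1 | 1.00 | 1.00 |

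In the rows with no survivor at 4-7, the outcome does not vary once deaths are dropped, so the estimate there reflects only the penalty. The fifth row avoids that, and the gap is smaller.

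**3. Ordinal model.** Assume active scores of five 1s, four 2s and one 3, and placebo scores of five 1s and three 2s plus two deaths. The odds ratio for a better score on active is 0.53 (p = 0.50) with deaths dropped and 1.29 (p = 0.77) with deaths scored 8. The estimate changes side, though neither result is informative at this size.

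**4. Chance that it arises.** P(at least one death among 30) = 1 - (1-p)^30. At assumed mortality of 3%, 5%, 10% and 20% this is 60%, 79%, 96% and 99.9%.

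**The case against.** The strongest reply is that the plan nowhere excludes deaths. Score 8 is defined, the worse Firth category runs to 8, and the change table reaches +4, which is what death gives from a baseline of 4. A known death is arguably not a blank field of requested data, so a programmer could assign 8 without breaching SAP 4.3.1. The eCRF is not available here and may capture the score. This stands as far as it goes: a reader who infers that the SAP prescribes a survivors-only comparison goes beyond the text. But it means that one SAP supports two data sets, and the literal reading is the one that loses the deaths.

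Second, SAP 4.3.1 and the default denominator in SAP 4.2 may keep every mITT patient in the percentages. That is fair for tables but does not reach a regression. The table could show 8 of 10 placebo patients at 0-3 while the model uses 8 of 8. Nor is 8/8 a recovery rate: recovery by Days 14 and 28 is a separate endpoint, and its denominator keeps patients who die unrecovered.

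Third, a reader might infer that mortality is hidden. It is not. All-cause mortality at Days 14, 28 and 60 is its own secondary endpoint (only listed if there are three or fewer deaths), and fatal events are summarised under safety.

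Fourth, the stakes are modest. SAP 4.9.2 treats all p-values as exploratory. Even with deaths scored, 10/10 against 8/10 gives a two-sided Fisher p of 2 × 45/190 = 0.47, and an approximate 95% interval around 6.18 runs from about 0.3 to 150. This limits the consequence but does not make the estimate right.

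A reader might also extend the point to intubated patients, because Protocol 4.1.1 speaks of WHO collection "on Days 5, 7, 10, 14 and weekly thereafter". The documents do not settle that. The same sentence defers to the Schedule of Assessments, and Table 1 schedules the score daily from Day 2 to Day 7. Days 2, 3, 4 and 6 are not regression days in any case.

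**Conclusion.** The point holds as a gap with a default that works against the endpoint. No rule assigns score 8 after death, and the stated rules, followed literally, remove earlier deaths from the by-visit ordinal and Firth models and from the bar chart. Tables and models may then rest on different patients.

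The size depends on how many deaths occur and how they split between arms, which the documents do not give. With about 10 per arm, one to three deaths all in one arm move the illustrative Firth odds ratio from 1.11-1.40 to 3.32-9.80, or from 0.81 to 0.16 when two deaths fall on active. Equal deaths in otherwise identical arms move nothing. The primary endpoint is treatment-emergent adverse events and is unaffected. This is a clarification that should be made before the WHO regressions are interpreted. It does not threaten the trial's main conclusions.

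**What to change.** Add to SAP 4.9.4.1 that, from the date of death through Day 60, WHO score 8 is assigned at every analysis visit, in the by-visit tables, shift tables, bar chart, ordinal regression and Firth regression. Exempt this assignment explicitly from the no-imputation rule in SAP 4.3.1. State that it overrides any earlier record mapped into the same window. Report the number of patients per arm entering each model and how many were scored 8 by this rule.

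The SAP's revision history already records changes made after unblinding in versions 2.0 and 3.0. This change should be recorded in the same way and labelled post hoc where SAP 3.2 requires.

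The cost is one sentence and one derivation step. Death dates are already needed for the mortality endpoint, so no new data are required.
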